### *Treatment of yaws:*

Single dose of Azithromycin (30mg/kg, max 2G).

### *Treatment of scabies:*

Either an oral dose of Ivermectin (200µg/kg) or permethrin cream for those with a contraindication to Ivermectin (WT<15kg, pregnant or breastfeeding women) given in 2 doses 7-14 days apart.

### *Site 1- Parallel Treatment Arm*

Single dose azithromycin (for yaws) and Ivermectin/Permethrin (for scabies) will be offered on D1. A second dose of Ivermectin/Permethrin will be offered 7-14 days later.

### *Site 2- Serial Treatment Arm*

Ivermectin/Permethrin (for scabies) will be offered on D1 with a second dose of Ivermectin/Permethrin offered 7-14 days later..

Single dose azithromycin (for yaws) will be offered at the twelve month follow-up visit.

## **3.1 STUDY OUTCOME MEASURES**

### Primary Outcome

a) Difference in the change in prevalence of impetigo between baseline and 12-months between the parallel and the sequential treatment arms.

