**Contact details for reporting SAEs and SUSARs**  
**[contact] / [name]**  
**Email: [contact]**

## 8. ASSESSMENT AND FOLLOW-UP

### Baseline Data Collection

At baseline (D1) all individuals will undergo a standardized examination to collect data on the presence of skin lesions consistent with yaws, scabies and impetigo. Following examination a finger-prick sample will be obtained from all individuals on to filter paper. In individuals with skin lesions consistent with yaws the same finger prick sample will be used for a rapid diagnostic test for yaws. In individuals with skin lesions consistent with yaws or impetigo two sterile lesion swabs will be obtained.

Following examination individuals will be weighed and directly observed treatment will be dispensed in line with standard treatment guidelines (see above). On D8 study teams will return to each community and offer a second dose of medication for scabies.

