## 9. STATISTICS AND DATA ANALYSIS

### *Sample Size*

The sample size required for our primary outcome was estimated as follows:

- Pre-MDA prevalence of impetigo of 25-30%
- Impetigo prevalence to fall to about 10% in the Ivermectin only arm
- Impetigo prevalence to fall to about 5% in the combined arm
- Enrolment 80%
- Loss to follow-up 10%
- 90% power to detect a difference between the two arms

Primary Outcome:

- a) Prevalence of impetigo at months 12 months in parallel treatment communities compared to sequential treatment communities.

Secondary outcomes:

- b) Change in the proportion of swab samples from which *S. pyogenes* is cultured between baseline and follow-up in the two arms
- c) Proportion of samples from which a drug-resistant isolate is cultured.

Data and all appropriate documentation will be stored for a minimum of 5 years after the completion of the study, including the follow-up period.

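### Neither wording of the primary outcome adjusts for Day 1 impetigo; read as an absolute difference in change, it has under half power, while against month-12 prevalence the gain is small

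*Combined protocol and SAP*

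**What the plan says.** The Study Summary and Section 3.1 word the primary outcome as a change from baseline: "Difference in the change in prevalence of impetigo between baseline and 12-months between the parallel and the sequential treatment arms". No scale (absolute or relative) and no estimator are given.

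Section 9 words it as a month-12 comparison: "Prevalence of impetigo at months 12 months in parallel treatment communities compared to sequential treatment communities". Baseline does not enter.

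Section 9 lists planning assumptions and outcomes, but no model, covariate or method for community clustering. Section 5.1 randomises communities; their number is not given.

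The baseline measurement exists. Section 8 states: "At baseline (D1) all individuals will undergo a standardized examination", and that examination covers yaws, scabies and impetigo.

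**The concern.** There are three usual ways to treat a baseline: subtract it, ignore it, or adjust for it. The protocol words its primary outcome in the first way in one place and in the second way in another. It never specifies the third, which is generally the most efficient and uses data already collected.

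Subtraction on the absolute scale is a poor choice with these prevalences. At 25–30% the baseline has a larger binomial variance than the month-12 outcome at 5–10%, so subtracting it adds more noise than it removes. Ignoring the baseline avoids that loss. It leaves any chance difference in starting prevalence in the month-12 comparison, and such differences are larger when whole communities are randomised. At stake is the precision with which the trial can detect its planned 5-point azithromycin effect.

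**Working it through.** **Inputs from the documents.** Section 9: "Pre-MDA prevalence of impetigo of 25-30" (per cent); "Impetigo prevalence to fall to about 10% in the Ivermectin only arm"; "Impetigo prevalence to fall to about 5% in the combined arm"; "90% power to detect a difference between the two arms"; 10% loss to follow-up. Study Summary: 637 per arm.

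**Assumed.** Two-sided 5% test; within-person correlation r between baseline and month-12 status of 0 to 0.3; the same people seen at both visits; no clustering.

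**1. The plan's own figure.** Comparing 10% with 5% at 90% power:
- Pooled variance gives 582 per arm; 582/0.9 = 647 and 582 × 1.1 ≈ 641.
- Unpooled: (1.96 + 1.2816)² × (0.09 + 0.0475)/0.05² ≈ 578; 578 × 1.1 ≈ 636.

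These bracket 637. It is therefore consistent with a plain individual-level month-12 comparison. No baseline term or design effect is needed to reach it.

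**2. Standard error and power at 637 × 0.9 ≈ 573 per arm.** Let v0 = b(1−b) for baseline prevalence b, and v = 0.09 (sequential arm) or 0.0475 (parallel arm).
- Month 12 only: variance = (0.09 + 0.0475)/573 = 0.1375/573.
- Absolute change: variance = Σ[v0 + v − 2r√(v0·v)]/573.
- Adjusted: variance = 0.1375(1 − r²)/573.

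Example, b = 0.25 and r = 0: change variance = (2 × 0.1875 + 0.1375)/573 = 0.5125/573, SE 2.99 points. Month 12 only: SE 1.55 points.

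| b | r | SE change (points) | Power change | Power month 12 | Power adjusted |
|---|---|---|---|---|---|
| 25% | 0 | 2.99 | 39% | 90% | 90% |
| 25% | 0.3 | 2.57 | 49% | 90% | 92% |
| 30% | 0 | 3.12 | 36% | 90% | 90% |
| 30% | 0.3 | 2.69 | 46% | 90% | 92% |

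The change variance is 3.0 to 4.1 times the adjusted variance.

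**3. Does this depend on r?** The direction does not, at person level. In a given arm, subtraction beats month 12 alone only if r > √v0/(2√v). That is 0.72–0.76 (sequential) and 0.99–1.05 (parallel). The largest r possible for two binary variables with these prevalences is √[p(1−b)/(b(1−p))], where p is month-12 prevalence: 0.51–0.58 and 0.35–0.40.

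**4. Does it depend on scale?** Yes. On the log-risk scale the per-person variance is (1−p)/p: 9 and 19 at month 12, but only 2.3–3.0 at baseline. With effect ln 2 = 0.693, b = 0.25 and r = 0, the SE of the difference in log-risk change is √[(9 + 19 + 2 × 3)/573] = 0.244, giving 81% power. Over the same ranges of b and r, power is 81–90% for relative change, 88% for month 12 alone and 88–91% adjusted.

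**5. Chance imbalance.** At 637 per arm the baseline difference has SE √(2 × 0.25 × 0.75/637) = 2.4 points, or 2.6 at 30%. Its 95% range is about ±5 points before clustering. As an illustration, take no azithromycin effect, the same proportional fall in both arms (10/27.5 = 0.364), and baselines of 30% (parallel) and 25% (sequential). Month 12 is then 10.9% v 9.1%, which is 1.8 points against the parallel arm. The absolute falls are 19.1 and 15.9 points, which is 3.2 points in its favour. The relative falls are equal.

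**The case against.** The strongest objection is that the large power loss belongs to one reading only. Section 3.1 names no scale, and on a relative scale most of the loss goes. The same is seen at community level. With 6 communities per arm, baseline SD 4–7 points and residual CV 0.2–0.4 (all assumed), simulated power was 43–63% for relative change and 39–63% for baseline adjustment, against 17–24% for absolute change. This stands, and the conclusion is limited accordingly.

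Second, 637 is consistent with the Section 9 comparison. Against that version, adjustment adds only 0–2.5 power points at person level and is roughly neutral at community level. With as few as 3 communities per arm it can cost power. This also stands.

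Third, a reader might infer from the 3.2-point illustration that the planned analysis is biased or would manufacture a benefit. The documents do not support that. Communities are randomised, so both comparisons are unbiased on average, and a valid standard error covers chance imbalance. The illustration also uses 25–30%, which in Section 9 is planning uncertainty about overall prevalence and not a predicted difference between arms.

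Fourth, a reader might infer that the plan rules out adjustment. It does not: it names outcomes, not estimators. Adjustment is unspecified. In an open-label trial that is still a reason to settle it in advance.

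**Conclusion.** The point holds in a limited form. Neither primary definition uses Day 1 impetigo as a covariate, though it is collected from everyone. If the Section 3.1 outcome is analysed as an absolute difference in change, power for 10% v 5% falls from about 90% to about 36–49%, and adjustment would give 90–92%. This rests on 573 evaluable per arm, baseline 25–30%, r of 0–0.3 and no clustering. Clustering would lower power for every version; with large, stable community differences, change could outperform unadjusted month-12 prevalence.

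It would go too far to say that power is halved whichever wording is kept. On a relative scale the loss is at most about 7 points (81% v 88%). Against Section 9 the gain is small, and the reason to adjust is to correct chance imbalance in the one allocation that occurs.

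**What to change.** In Sections 3.1 and 9, and in the Study Summary, state one primary estimand: month-12 impetigo compared between arms. Estimate it in a model that contains arm and Day 1 impetigo (participant status for those seen at both visits, community Day 1 prevalence, or both) and accounts for community randomisation. Report change from baseline descriptively.

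State the number of communities. If they are few, adjust for participant-level Day 1 status only, or keep arm in the community-level model.

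A tempting alternative is to fit community Day 1 prevalence in a first-stage model without arm and then compare residuals. That pulls the effect toward zero. With k communities per arm, chance alone gives an expected squared correlation of 1/(2k−1) between arm and covariate. A true 5.0-point effect therefore averages 5 × (1 − 1/5) = 4.0 with 3 per arm and 5 × (1 − 1/11) ≈ 4.5 with 6. Simulation agreed, and a model that keeps arm returned 5.0.

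Cost: a few sentences and one model, with no new data, visits or participants. The downside is that a community-level covariate uses one degree of freedom, which matters if communities are few.

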### Secondary Outcomes

b) Change in the proportion of swab samples from which *S. pyogenes* is cultured between baseline and follow-up in the two arms

c) The proportion of samples from which a drug-resistant isolate of *S.pyogenes* is cultured in the two arms

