### **1.2 RATIONALE FOR CURRENT STUDY**

Current WHO recommendations for yaws are for community mass treatment with single dose azithromycin[3]. The impact of this treatment on other bacterial skin diseases is unknown.

Azithromycin has activity against both *S. pyogenes* and *S. aureus* and mass treatment with azithromycin, for either yaws or trachoma control, might have additional impacts on both the prevalence of impetigo and the potential emergence of resistant organisms. These issues may be of particular relevance in the Pacific where mass treatment for yaws or trachoma is likely to be conducted in the near future and where scabies and impetigo are also both common.

Understanding the impact of azithromycin mass treatment on impetigo will inform whether integrated control programmes for yaws, trachoma and scabies could be considered in the Pacific where all three diseases are endemic.

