## 2. STUDY OBJECTIVES

### Study Aims:

Assess the impact of single dose azithromycin, given for yaws, on other prevalent bacterial skin infections.

Assess the impact of single dose azithromycin on antimicrobial resistance patterns in isolates of *S.pyogenes* and *S.aureus*.

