### Secondary Objectives:

The secondary objective is to assess whether treatment with a single dose of azithromycin results in change in the anti-microbial susceptibility of clinical skin swab isolates .

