### Interim Visit

At Month 3 an interim visit will be made. Individuals will be re-examined and swabs collected from those with clinical evidence of impetigo. Data from previous studies indicates that scabies and impetigo continue to decline between month 3 to month 12 following community mass treatment for scabies therefore treatment will not routinely be offered at this time point.

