### Laboratory Work

- Dried blood spots will be eluted at tested using the Treponema Pallidum Haemagglutination Assays.
- From each pair of lesion swabs, one swab will be tested using culture and anti-microbial sensitivity testing for *S. pyogenes* and *S. aureus*.

- The second lesion swab will be tested using molecular techniques to assess the microbiological flora of the lesions.

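### Resistance outcome (c) only partly serves the isolate-based aim: Section 3.1 has no S. aureus outcome, Section 9 names no organism, and the denominator is samples

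*Combined protocol and SAP*

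**What the plan says.** - **Aim** (Summary; Section 2, Study Aims): "Assess the impact of single dose azithromycin on antimicrobial resistance patterns in isolates of" S. pyogenes and S. aureus. Section 1.2 discusses the same two organisms and says that mass azithromycin "might have additional impacts on both the prevalence of impetigo and the potential emergence of resistant organisms".
- **Secondary objective** (Section 2): whether a single dose "results in change in the anti-microbial susceptibility of clinical skin swab isolates". The unit is the isolate, and no organism is named.
- **Outcome (c)** (Summary; Section 3.1): "The proportion of samples from which a drug-resistant isolate of" S. pyogenes is cultured, in each arm. Outcome (b), the change in culture-positive swabs, is also for S. pyogenes alone.
- **Outcome (c) in Section 9:** "Proportion of samples from which a drug-resistant isolate is cultured", with no organism.
- **Laboratory Work** (Section 8): of each pair of swabs, "one swab will be tested using culture and anti-microbial sensitivity testing for" S. pyogenes and S. aureus.
- **Who is swabbed** (Section 8, Baseline Data Collection, with the same rule under Follow-Up Data Collection): "In individuals with skin lesions consistent with yaws or impetigo two sterile lesion swabs will be obtained".

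**The concern.** There are two separate gaps between the aim and the outcome.

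The first is the organism. The aim covers two species and the laboratory tests both, but the outcome list in the Summary and Section 3.1 covers one. Section 9 can be read either way. Whether an S. aureus resistance result is a planned outcome therefore depends on which section the analyst follows, and in an open-label trial that should not be settled after the cultures are read.

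The second is the denominator. The aim and objective ask about resistance among isolates, whereas (c) counts samples. A sample counts towards (c) only if the organism grows and the isolate is resistant, so (c) combines two quantities. One of them, recovery, is something the trial itself treats as able to change, since it is outcome (b). Taken alone, a difference or a lack of difference in (c) between arms cannot be attributed to resistance.

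**Working it through.** The plan gives no culture yield, resistance rate or sample size for (c), so there is no stated figure to reproduce.

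**1. Organism, by place in the plan**

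| Place | Unit | Organism |
|---|---|---|
| Aim (Summary, Section 2) | isolates | S. pyogenes and S. aureus |
| Secondary objective (Section 2) | isolates | not named |
| Outcome (c), Summary and Section 3.1 | samples | S. pyogenes |
| Outcome (c), Section 9 | samples | not named |
| Laboratory Work (Section 8) | one swab of each pair | S. pyogenes and S. aureus |

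No outcome definition uses isolates as the denominator, and none names S. aureus.

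**2. What the per-sample measure contains**

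P(resistant isolate per sample) = P(culture positive) × P(resistant, given an isolate).

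All rates below are assumed. Recovery in the sequential arm is fixed at 60% and its resistant share at 5%, so (c) = 0.60 × 0.05 = 3.0%.

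| Parallel-arm recovery | Parallel-arm resistant share | (c), parallel arm | Per-sample ratio | Per-isolate ratio |
|---|---|---|---|---|
| 60% | 10% | 6.0% | 2.0 | 2.0 |
| 30% | 10% | 3.0% | 1.0 | 2.0 |
| 15% | 10% | 1.5% | 0.5 | 2.0 |
| 30% | 5% | 1.5% | 0.5 | 1.0 |

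With equal recovery the two measures agree. With unequal recovery a true doubling can look like no change or a halving, and an unchanged share can look like a halving.

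**3. Can the share be recovered from the listed outcomes?**

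For S. pyogenes, yes. The swabbing rule is the same at baseline and month 12, and one swab per pair is cultured. Dividing (c) by the culture-positive proportion underlying (b) at the same visit gives the resistant share of S. pyogenes-positive samples. In the second row this is 3.0/30 = 10% against 3.0/60 = 5%, so the doubling is visible.

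For S. aureus, no. Even if Section 9 is read to include it, (b) gives no S. aureus recovery to divide by.

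**4. How many isolates to expect at month 12**

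Inputs: 637 per arm (Summary); 10% loss to follow-up, and impetigo prevalence of about 5% (combined treatment) and 10% (ivermectin only) at month 12 (Section 9). The 637 is taken as people enrolled. Positivity for an organism is assumed to be 30-70%, and only impetigo lesions are counted.

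- Followed: 637 × 0.9 = 573.
- Parallel arm: 573 × 0.05 = 29 people; × 0.30 to 0.70 = about 9 to 20 isolates.
- Sequential arm: 573 × 0.10 = 57 people; × 0.30 to 0.70 = about 17 to 40 isolates.

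If the 80% enrolment figure also had to be applied to 637, then 637 × 0.72 = 459 would be followed, giving about 7 to 16 and 14 to 32 isolates. Yaws-like lesions would add some swabs, but the plan gives no number for them.

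**The case against.** Several points on the other side stand.

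- A per-sample proportion is a legitimate measure of the burden of resistant infection and informs part of the aim. The per-isolate share has its own weakness: it can rise merely because susceptible strains have been removed. A reader might infer that (c) fails to answer the aim. The documents support only that it is incomplete for it.
- For S. pyogenes the share follows from (b) and (c) at one visit, so for that organism the denominator is largely a matter of presentation.
- A reader might infer that the plan will yield no S. aureus resistance result at all. That is too strong. Section 9 names no organism, and since both species are tested, its literal wording could include S. aureus. It may equally be shorthand for the Section 3.1 wording, and nothing in the plan settles which.
- A reader might infer that (c) will hide a rise in resistance. No rate in the documents shows this. Only people with lesions are swabbed, so a fall in impetigo prevalence does not by itself imply lower recovery per swab. Exact cancellation, as in the second row of the table, is one assumed case.

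What remains is that S. aureus has no outcome in the Summary or Section 3.1, Section 9 is ambiguous, and no listed outcome reports the quantity that the aim describes.

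**Conclusion.** The point holds as a fault of definition, not of data collection. The Summary and Section 3.1 omit one of the two organisms in the aim, Section 9 leaves the organism open, and the per-sample denominator answers an isolate-based aim only in part. The organism mismatch is plain from the text.

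The size of any distortion from the denominator is unknown. For an assumed doubling of the resistant share, with recovery of 60% in one arm and 15-60% in the other, the per-sample ratio lies between 0.5 and 2.0. The upper end applies when recovery is equal and there is no distortion.

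The primary outcome is not affected. The change is worth making because it concerns one of two stated aims and uses cultures that are already planned.

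**What to change.** Word (c) identically in the Summary, Section 3.1 and Section 9: the proportion of tested isolates that are drug-resistant, separately for S. pyogenes and S. aureus, by arm, at baseline and month 12. Keep the per-sample proportion alongside as a measure of burden, so that a rise in the share caused by loss of susceptible strains can be recognised.

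Report numerators and denominators and label the result descriptive. Communities are randomised (Section 5.1), so any interval should either allow for clustering by community or state that it does not.

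The cost is wording in three places and a few extra tables, with no new visit, swab or assay. The drawback is imprecision. With about 9-40 isolates per arm at month 12, exact 95% intervals that treat isolates as independent would be, for example, 0.3-48% for 1/9 and 6-30% for 6/40. The re-worded outcome could not reliably distinguish a share of 5% from one of 10% and should not be presented as a test of that difference.

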### **3.2 RISKS AND BENEFITS**

Mass treatment with azithromycin is the standard of care for yaws endemic communities. Several studies have demonstrated a reduction in both active and latent cases of infection[11,12]. Mass treatment for scabies with both Ivermectin and Permethrin has been shown to be an effective intervention at reducing the prevalence of scabies at a community level[10,13].

The safety profile of single dose azithromycin is well known. Azithromycin is considered the standard treatment for trachoma and yaws, both as therapy and in MDAs, and has been employed for over 10 years in trachoma control programs. An active population-based surveillance of multiple communities in Ethiopia found a low prevalence of AEs after mass azithromycin distribution. The most frequently observed AEs (between 1 and 10%) were nausea, vomiting and diarrhea.

The safety profile of ivermectin is also very well known. Safety has been well studied through its usage therapeutically and in large scale MDA programs. In the past 21 years, more than 1 billion doses of ivermectin tablets have been distributed for both onchocerciasis and lymphatic filariasis, at doses of 100-200 µg/kg with excellent safety. A review of women accidentally given ivermectin while pregnant showed no evidence of teratogenicity.

Co-Administration of Azithromycin and Ivermectin was shown to be safe in the Azival study[14]. There was no difference in the number of adverse events in individuals who received combined treatment compared to those who received treatment one week apart. The safety of co-administration has recently been confirmed in the AIM study in which the rate of adverse events following combined Azithromycin and Ivermectin treatment was <5% and no SAEs were noted ([name], Personal Communication).

#### **Benefits to Communities**

Communities will benefit from receiving treatment for both scabies and yaws as part of these studies. These are both major public health problems in the Solomon Islands and participating communities will therefore gain benefit from receiving the best available treatment for these two conditions which it is believed will result in improvements in their health and well being.

